3.3 Benefit/Risk Assessment

Patients who undergo implantation of the Artegraft may benefit from immediate or earlier cannulation, to limit the time required for dialysis catheter use, with the potential serious adverse effects of septicemia, sepsis, and death. The proposed change is to allow for cannulation within 72 hours post implantation. The previous label required a minimum of 10 days be allowed after implantation before puncturing the graft with needles for hemodialysis. Early cannulation may be associated with an increase in bleeding, , hemorrhage, infection, and thrombosis during initial dialysis sessions. The potential increased risks associated with early cannulation and the information to evaluate these risks are presented (Table 4).

The risks anticipated in this study are similar to those associated with currently marketed synthetic and biologic prosthetic grafts used for dialysis. The superficial site of implantation of the Artegraft, when used for dialysis, facilitates clinical and regular ultrasound monitoring of the graft, allowing any such complication to be recognized and treated promptly, thus minimizing potential risk to the patient.

More detailed information about the known and expected benefits and risks and reasonably expected adverse events (AEs) of the Artegraft are in the Instructions for Use (Package Insert) in Appendix 8. The expected adverse device and procedure effects also are listed in the Safety section and in the Informed Consent. The expected events have been derived from clinical practice, literature reviews, clinicaltrials.gov results, and FDA PMA summaries for devices of this type.

Based on the risk information (Table 4), most risks are acute and identifiable during the immediate post-implantation period. We propose a multi-center, randomized, open-label treatment trial with a primary endpoint of successful Early Access, defined by three cannulations, the first one started within 72 hours post implantation, all with minimum dialysis flow rates of 250 ml/min, with a minimum 17-guage needle. Patients having cannulation within the definition of early access (i.e., within 72 hours) will be included in the primary analysis.

Artegraft will follow all study patients enrolled in the proposed clinical trial and that have successful cannulation within 72 hours as defined above, for 6 months. If follow-up is necessary at 1 year after graft implantation, it will be done via phone survey. The late-access group [>/= 10 days] will be followed to 30 days post-first cannulation. Day 0 is defined as the day of first cannulation, for early-access and late-access groups, to allow full follow-up to at least 30 days for both groups

Artegraft, Inc. Version 4.0 21June2019
Protocol: ARTCT.BEACH.001 CONFIDENTIAL Page 26 of 81

Table 5: Risk Analysis Associated with Early Access

| Risk | Timing of Potential Risk | Rating of Risk ¹ | Non- Clinical Testing ² | Relevant Clinical Endpoint |
|---|--|--------------------------------|--|---|
| Serious Graft Infection | Typically, between 0 (surgical or device) and 180 days (cannulation) | 3 | none | Requires Intervention |
| Serious Hemorrhage / Hematoma | Between initial cannulation and 10 days | 3 | none | Requires Intervention |
| Excessive needle hole bleeding ³ | After removal of each cannula | 1 | none | Requires Additional Direct Pressure Time |
| Occlusion; primary and secondary | Ongoing with A/V access | 3 | none | Requires Intervention ⁴ |
| Inability to Cannulate | Immediate and up to 10 days | 2 | none | Continual or need for dialysis catheter |

¹ Rating: 1=Minimal; 2=Mild; 3=Serious; 4=Life-threatening; 5=Death

3.3.1 Risk Mitigation

These risks will be minimized is a clinical manner applicable for all grafts and fistulas. These procedures are defined below:

- **Serious graft infection**: Standard of Care sterile procedures and antibiotic prophylaxis will be used during implantation. In addition, Standard of Care sterility procedures will be used during cannulation at the hospital or at the various outside dialysis centers.
- Serious Hemorrhage or Hematoma: Standard of care surgical procedures will be utilized during
 implantation to insure the suture lines are properly closed and Standard of Care tunneling
 technique will be used to insure graft incorporation. During cannulation Standard of Care
 procedures will be used to insure proper cannulation to avoid damage to the graft during needle
 insertion.
- Excessive Needle Hole Bleeding: This risk will be minimized by initial use of 17-gauge needles during cannulation with lower flow rates. Once the graft has healed-in, the needle size can be increased as Standard of Care dictates. After the needles are removed adequate digital pressure will be applied to stop bleeding through cannulation sites. In addition, investigators and/or research coordinators from each site will train dialysis staff to minimize this risk factor.

Artegraft, Inc. Version 4.0 21June2019
Protocol: ARTCT.BEACH.001 CONFIDENTIAL Page 27 of 81

² No preclinical test can be used to evaluate these clinical parameters

³ Excess is defined as bleeding for >10 minutes using digital pressure

⁴This is routine procedure for A/V access grafts (e.g., thrombectomy)

- Occlusion Primary and Secondary: As mentioned previously, occlusion of access grafts and
 fistulas is a common occurrence. It will be minimized using Standard of Care 17-gauge needles and
 the use of the largest vein on the upper arm, preferably the axillary vein to maximize blood flow
 through the graft.
- Inability to Cannulate: To minimize the risk of the inability to cannulate, the graft will be implanted near the skin, which is Standard of Care so that the graft can be easily palpated prior to needle puncture. In addition, as will be discussed later, the investigator or research coordinator at each site will meet with dialysis personnel to discuss the nature of the study and any cannulation requirements, such as the initial use of 17-gauge needles.

Artegraft, Inc. Version 4.0 21June2019
Protocol: ARTCT.BEACH.001 CONFIDENTIAL Page 28 of 81

4.0 OBJECTIVES AND ENDPOINTS

Table 6: Study Objectives and Endpoints

| able 0. Study Objectives and Endpoints | | | | |
|---|---|--|--|--|
| Study Objective | The objective of the BEACH Trial is to demonstrate that early access of Artegraft is associated with acceptable rates of successful early access, and acceptable rates of a composite of adverse events, to support a modification of existing device labeling stating that Artegraft is capable of cannulation within 72 hours post implantation. | | | |
| Primary Effectiveness Endpoint | Early access success, defined by three cannulations, the first one started within 72 hours post implantation, all with minimum dialysis flow rates of 250 ml/min pump flow rate, with a minimum 17-guage needle. | | | |
| | Expectations: $^{\sim}80\%$ of patients in the early access group will have first cannulation within 72 hours. | | | |
| | Expectations: ~90% of patients receiving early access will have 3 successful cannulations. | | | |
| Primary Safety Endpoint | A composite of major adverse clinical events (MACE) including perigraft infection, hemorrhage, thrombosis, steal syndrome, and pseudoaneurysm within 30 days after first cannulation [Day 0] in the early-access and late-access groups. | | | |
| | Expectation: ~20% of patients will have at least one MACE event; no significant difference in event number or type between early and late access groups. | | | |
| | All MACE will be adjudicated by an independent accessor. | | | |
| Secondary Effectiveness Endpoints | Patency (Primary, Assisted Primary, and Secondary) at 30 days after first successful cannulation [Day 0], and at 12 weeks and 6 months after implantation in the early-access group and at 30 days post-Day 0 in the lateaccess group. The late access group will also be assessed for patency at 6 months through a telephone interview or office visit to provide a more robust data set. | | | |
| | Expectations: | | | |
| | Patency rates [all 3 types] at 30 days will be similar in the early and late access groups. | | | |
| | We expect primary patency to be ≥85%, ≥75% and ≥65% at 30 days, 3 months, and 6 months, respectively. | | | |
| | Primary-assisted patency rates at 30 days, 3 months, and 6 months will be ≥85%. | | | |
| | Secondary patency rates will be ≥90% and ≥90% at 3 and 6 months, respectively. | | | |

Artegraft, Inc.
Protocol: ARTCT.BEACH.001

Version 4.0 CONFIDENTIAL 21June2019 Page 29 of 81

| Secondary Safety (for information only) | All adverse events will be collected in the early-access group [to 6 months] and the late-access group [to 30 days post Day 0] and summarized by unique event, seriousness, and relationship to device or procedure. All serious adverse events will be adjudicated by an independent accessor. |
|--|---|
| Secondary Catheter Removal Endpoint (for information only) | The number of days from graft implant or fistula revision to catheter removal shall be recorded. |

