| Patient Number | A total of 50 patients will be randomized to early access, successfully provided early cannulation within 72 hours, and will be followed to 6 months, to provide the data required for submission to the FDA. A 12month assessment for unexpected complications will also be obtained for early access subjects. Patients randomized to the early access group who are not cannulated in the <72-hour period will be followed as a late-access subject |

Artegraft, Inc.
Protocol: ARTCT.BEACH.001

Version 4.0 CONFIDENTIAL 21June2019 Page 9 of 81

| | for 30 days after first cannulation. It is estimated that up to 10 additional patients may fall into this category. A total of 25 patients will be randomized to late access, cannulated at 10 days or later after implant and followed for at least 30 days after first cannulation [Day 0] to assess perioperative major adverse clinical events (MACE) rates and patency data. The late access group will also be assessed for patency at 6 months through a telephone interview or office visit to provide a more robust data set |
|---|---|
| Intervention Description | Patients will be implanted with the Artegraft, for vascular cannulation for hemodialysis, using standard vascular techniques, according to the Instructions for Use. |
| Number of Investigators and Study Centers | Up to five (5) investigational sites are expected to participate in the trial. |
| Study Duration | The enrollment goal is ≥3 patients per site, per month. The anticipated enrollment period is 6 months; the patient enrollment duration for early-access patients is a minimum of 6 months, and total study duration is expected to be 12 months. |
| | The follow-up period on the early access patients will be 6 months and 30 days on the late access patients. In addition, a follow-up telephone call, based on a questionnaire, will be made to the early access patients and/or dialysis centers to determine if any unexpected complications had occurred during the 6-12-month period. For this reason, all patients will be consented to 12 months. The late access group will also be assessed for patency at 6 months through a telephone interview or office visit to provide a more robust data set. |
| Primary Effectiveness Endpoint | Early access success, defined by three cannulations, the first one started within 72 hours after implantation, all with minimum dialysis flow rates of 250 ml/min pump flow rate, with a minimum 17-gauge needle. |

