| 12-Lead ECG, when medically indicated | X | | | | | | |
| Vessel mapping (if not done within 8 weeks) | Х | | | | | | |
| Pregnancy test: serum (Women of child-bearing potential only; to be assessed within 7 days of implant) | Х | | | | | | |
| Hematology and coagulation lab test | Х | | | | | | |
| Surgical implant of Artegraft | Х | | | | | | |
| Documentation of surgical procedure | X | | | | | | |
| Assessment of wound healing | | Х | Х | Х | Х | Х | |
| Graft Patency Assessment | Х | Х | Х | Х | Х | Х | Х |
| Adverse event assessment | Х | Х | Х | Х | Х | Х | X ⁺ |
| Medical Device malfunctions | Х | Х | Х | Х | Х | Х | |
| Documentation of graft interventions | X | Х | Х | Х | Х | Х | |
| Use of Dialysis Catheter | | Х | Х | Х | Х | Х | |

These patients will be having dialysis every few days – assessments should be the same or similar at each post-implant visit.

^{*} Extended follow-up will be assessed for patency and AEs only via a telephone follow-up or office visit

⁺ AEs between 6 months and 12 months.

Table 2b: Schedule of Assessments (SoA) Late Access and Early Access Drop-outs

| Procedure | Screening Day -45 to Day of Surgery | Day 0 [1st successful cannulation] (May occur on day of surgery) | Day 1 – 17 Days post Day 0 | Day 30 +/- 3 days post Day 0 | 6 Months +/- 7 days post day 0* Extended Duration Follow-up |
|--|--|---|----------------------------------|--|---|
| Eligibility (inclusion/exclusion) | Х | | | | |
| Informed Consent | Х | | | | |
| Medical History | Х | | | | |
| Prior and concomitant medication | Х | | Х | Х | |
| Physical Exam | Х | | X | Х | |
| 12-Lead ECG, when medically indicated | Х | | | | |
| Vessel mapping (if not done within 8 weeks) | Х | | | | |
| Pregnancy test: serum (Women of child-bearing potential only; to be assessed within 7 days of implant) | X | | | | |
| Hematology and coagulation lab test | Х | | | | |
| Surgical implant of Artegraft | Х | | | | |
| Documentation of surgical procedure | Х | | | | |
| Assessment of wound healing | | Х | Х | Х | |
| Graft Patency Assessment | Х | Х | Х | Х | Х |
| Adverse event assessment | Х | Х | Х | Х | X ⁺ |
| Medical Device malfunctions | Х | Х | Х | Х | |
| Documentation of graft interventions | Х | Х | Х | Х | |
| Use of Dialysis Catheter | | Х | Х | Х | |

These patients will be having dialysis every few days – assessments should be the same or similar at each post-implant visit.

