^{**} Late access patients will be assessed for patency and AEs only via a telephone follow-up or office visit

⁺ AEs during time between 1 month and 6 months

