- Concomitant medication
- Medical device malfunctions
- Documentation of graft interventions
- Dialysis catheter status and use

8.5 12 weeks ± 7 Days Post Day 0 (early-access subjects only)

- Physical Exam
- Assessment of wound healing
- Graft patency assessment
- Adverse event assessment
- Concomitant medication
- Medical device malfunctions
- Documentation of graft interventions
- Dialysis catheter status and use

8.6 6 months ± 7 Days Post Day 0 (early access subjects only; late-access subjects will be assessed for patency only)

- Physical Exam
- Assessment of wound healing
- Graft patency assessment
- Adverse event assessment
- Concomitant medication
- Medical device malfunctions

- Documentation of graft interventions
- Dialysis catheter status and use

8.7 12 months ± 14 Days Post Day 0 (early access subjects only)

- Graft patency assessment
- Adverse event assessment between 6 months and 12 months

Artegraft, Inc.
Protocol: ARTCT.BEACH.001

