9.2 Statistical Methods

9.2.1 Overview of Statistical Analysis

Descriptive statistics will be performed separately for the early and late access treatment groups. The estimated patency rates will be calculated using the SVS reporting standards guidelines.³¹ Should there be considerable site differences and with sufficient number of patients within sites, stratified and/or weighted estimates may be performed.

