10.1 Safety Assessments

10.2 Adverse Events

The definitions of SAE can be found in Appendix 4.

Adverse events will be reported by the patient (or, when appropriate, by a caregiver, surrogate, or the participant's legally authorized representative) or may be obtained from the patient's dialysis center.

The Investigator and any designees are responsible for detecting, documenting, and recording events that meet the definition of an AE or SAE and remain responsible for following up AEs that are serious, considered related to the study device or study procedures, or that caused the subject to discontinue the Artegraft device(see Section 8.0 Study Procedures).

Expected Adverse Events

Table 9: Expected Procedure-Related Adverse Events

| Bleeding |
|--|
| Death |
| Disruption or tearing of the suture line, graft, or host vessel |
| Embolism |
| Graft redundancy |
| Intervention complication (e.g., venous rupture) |
| Occlusion |
| Pain |
| Thrombosis |
| Technical complications (anastomosed to diseased vessel; graft physically compressed; incorrect sizing; implant technique; radiology infiltrated graft; bleeding from native vessel) |

Artegraft, Inc. Version 4.0 21June2019
Protocol: ARTCT.BEACH.001 CONFIDENTIAL Page 47 of 81

Table 10: Expected Device-Related Adverse Events

| Access failure; loss of access |
|--|
| Aneurysm |
| Bleeding |
| Cannulation-associated complication / trauma |
| Death |
| Embolic event |
| Graft dilatation |
| Hand ischemia, acute |
| Hand ischemia, subacute (delayed but w/in 1 month of implant) |
| Hematoma |
| Hemorrhage |
| Infection (cellulitis, abscess, septic emboli, bacteremia, sepsis) |
| Intervention (surgical, angioplasty, stenting, thrombectomy, thrombolysis, revision) |
| Inflammation / sensitivity to device materials |
| Invasive surgical procedure |
| Kinking |
| Low flow |
| Neointimal hyperplasia |
| Pain |
| Primary graft failure |
| Pseudoaneurysm |
| Seroma |
| Skin erosion; lesion |
| Slow wound healing |
| Steal syndrome |
| Stenosis |
| Swelling of the implanted limb |
| Thrombosis / occlusion, graft |
| Thrombosis, other |
| Ultrafiltration |

All AEs will be collected from the start of treatment until the final follow-up visit at the time points specified in the SoA's (Table 1a and Table 1b).

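### The secondary safety summary gives the two arms unequal adverse-event windows, the schedule contradicts it on when late-arm collection ends, and no common window is set for the by-arm tables

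*Combined protocol and SAP*

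**What the plan says.** The endpoint text and the visit schedule disagree on how long late-arm AEs are collected.

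- **Endpoint text.** Table 6 in Section 4.0, like the summary in Section 1.0, reads "All adverse events will be collected in the early-access group [to 6 months] and the late-access group [to 30 days post Day 0". The AEs are then summarised by event, seriousness and relationship. The row is labelled "Secondary Safety (for information only".
- **Section 8.6.** At the 6-month visit, "late-access subjects will be assessed for patency only".
- **Late-access schedule in Section 1.0** (captioned Table 2b; Section 10.2 calls it Table 1b). It marks an AE assessment at 6 months. Its footnotes say the assessment covers months 1 to 6 and add: "Late access patients will be assessed for patency and AEs only via a telephone follow-up or office visit".
- **Section 10.2.** "All AEs will be collected from the start of treatment until the final follow-up visit at the time points specified in the SoA's". This ties AE collection to the schedules.
- **Early-access schedule (Table 1a) and Section 8.7.** These add a 12-month contact for "AEs between 6 months and 12 months".

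On analysis, Section 9.2.1 says "Descriptive statistics will be performed separately for the early and late access treatment groups". Section 10.2.8 names only the analysis set. No section gives a common cut-off, a patient-time denominator or a rule for AEs seen in only one arm. Section 9.1 rules out formal hypothesis testing.

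**The concern.** An AE percentage depends on how long patients are watched. If the by-arm table follows the endpoint text, the early column holds about six months of events and the late column little more than one. A higher early percentage could then come from follow-up length alone, and the table could not show how much of it did.

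This is the only planned summary that covers all AEs, and the trial is meant to support a label change for early cannulation. The distortion runs against the device. It would also make a real later excess hard to recognise, because no late-arm data over the same period would stand beside it.

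**Working it through.** The plan states no AE rate, power or formula-based sample size, so there is no planned figure to reproduce.

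**Step 1: length of observation.** Section 1.0 says "A total of 25 patients will be randomized to late access, cannulated at 10 days or later after implant", with no upper limit.

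- Late, endpoint text: at least 10 + 30 = 40 days from implantation.
- Early, endpoint text: 6 months, about 183 days, or 183 + 3 = 186 days if the clock starts at a Day 0 that falls at 72 hours.
- Ratio: 183/40 = 4.6 to 186/40 = 4.7. If late first cannulation were at day 28 (an assumption), it would be about 3.2.

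**Step 2: the possible readings.**

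| Reading | Early arm | Late arm | Like for like? |
|---|---|---|---|
| Endpoint text and Section 8.6 | 183–186 days from implantation | at least 40 days from implantation | No: length |
| Both schedules in full | 12 months post Day 0 | 6 months post Day 0 | No: length |
| Early cut at 6 months, late by its schedule | 6 months | 6 months | Length yes, ascertainment no |

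On the third reading, the early arm has scheduled 12-week and 6-month visits with physical examination. The late arm has one contact, possibly by telephone, covering five months.

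**Step 3: crude incidence in identical arms on the first reading.** Let p be the proportion with an event by day 30.

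- Constant hazard: h = −ln(1 − p)/30 and F(t) = 1 − exp(−h·t).
- Front-loaded: the hazard after day 30 is g·h, so F(t) = 1 − exp(−h·[30 + g·(t − 30)]) for t above 30.
- Patency course: Table 6 expects primary patency of 85%, 75% and 65% at 30 days, 3 months and 6 months. These are placed at days 30, 84 and 183 and interpolated log-linearly. Loss by day 40 is 1 − 0.85·(0.75/0.85)^(10/54) = 16.9%; by day 183 it is 35.0%.

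| Time course | Late, 40 days | Early, 183 days | Ratio |
|---|---|---|---|
| Constant, p = 5% | 6.6% | 26.9% | 4.1 |
| Constant, p = 10% | 13.1% | 47.4% | 3.6 |
| Constant, p = 20% | 25.7% | 74.4% | 2.9 |
| Constant, p = 40% | 49.4% | 95.6% | 1.9 |
| Constant, p = 60% | 70.5% | 99.6% | 1.4 |
| p = 20%, g = 0.5 | 22.9% | 54.7% | 2.4 |
| p = 20%, g = 0.25 | 21.5% | 39.8% | 1.9 |
| p = 20%, g = 0.1 | 20.6% | 28.6% | 1.4 |
| p = 20%, g = 0 | 20.0% | 20.0% | 1.0 |
| Primary-patency expectations | 16.9% | 35.0% | 2.1 |

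The 20% is borrowed from the MACE expectation in Table 6. The other values of p, and all values of g, are assumptions.

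**Step 4: two simple remedies that do not work.**

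- *A window of 30 days from implantation.* Early patients cannulated within 72 hours have 27 to 30 days after cannulation in it. Late patients have at most 30 − 10 = 20. Late-arm cannulation events would be cut off.
- *Events per patient-month over all follow-up.* Suppose the hazard falls to a quarter after day 40, with windows of 40 and 186 days. The early arm's average rate is then (40 + 146/4)/186 = 0.41 of the late arm's. With half the hazard it is (40 + 146/2)/186 = 0.61. Identical arms would make early access look safer, so the bias is reversed rather than removed.

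**Step 5: the window that works.** From Day 0 to 30 days post Day 0, both arms have the same length after cannulation, and identical arms have an expected ratio of about 1.0. Counting from implantation up to that same endpoint would not match: 30 to 33 days early against at least 40 late. The interval before Day 0 therefore needs its own table.

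**The case against.** The strongest counter-argument is that the late-access schedule does collect AEs from 1 to 6 months and that Section 10.2 makes the schedules govern. A reader who sees only the endpoint text might infer that late-arm AE observation definitely stops at about day 40. The documents do not support that: it is one of two conflicting statements. This part of the objection stands, and the contradiction itself belongs in the point. It does not clear the plan, because even on the schedule's terms ascertainment after day 30 differs between arms, and the early arm alone goes on to 12 months.

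A reader might also infer that early access is bound to look much worse, or that the trial's safety comparison is biased. Neither follows. Section 3.3 describes most risks as arising soon after implantation, which pulls the ratio towards 1.0. The primary safety endpoint, MACE, uses the same 30 days after Day 0 in both arms, and Section 9.2.2 reports it by arm and by component. The study objective is acceptable rates, and Section 9.1 compares observed with expected rates numerically, without a test. A real excess in the main early graft complications would therefore be visible on matched windows. What remains is the all-AE summary, where no matched window is set.

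**Conclusion.** The concern holds in limited form. The endpoint wording sets unequal AE windows, the schedule contradicts it for the late arm, and nothing in the plan supplies a common window.

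On the endpoint wording, identical arms would differ in crude incidence by about twofold if AEs followed the protocol's own primary-patency expectations. Across the scenarios tried, the ratio runs from 1.0 (no events after day 30) to 4.1 (a constant hazard with 5% by day 30). This rests on late cannulation at day 10 and on time courses borrowed from patency and MACE, since no AE rates are given.

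A further complication is that early-randomised patients not cannulated within 72 hours, estimated at up to 10, follow the shorter late-access schedule. If AEs are summarised as randomised, windows would be mixed within the early arm as well.

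The consequence is a descriptive table that could mislead. The primary safety result is not affected.

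**What to change.** 1. Reconcile Section 1.0 (endpoint summary), Section 4.0 and Section 8.6 with the late-access schedule and Section 10.2, so that one statement says when late-arm AE collection ends.
2. In Sections 9.2 and 10.2.8, make the by-arm AE tables cover Day 0 to 30 days post Day 0 in both arms, as for primary MACE. Show AEs from implantation to Day 0 separately by arm, because that interval differs by design.
3. Tabulate later AEs by interval: 30 days to 6 months, then 6 to 12 months for the early arm only. State the number observed and the method of ascertainment for each arm, and mark any period without late-arm data as having no comparator.
4. If rates per patient-time are given, give them within these intervals and do not pool them over unequal follow-up.
5. Show early-randomised patients not cannulated within 72 hours with their own follow-up window stated.

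The cost is wording and a few more tables, with no extra patients or visits. The small downside is that later early-arm AEs leave the main by-arm comparison.
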